## **J. Statistical Methods**

**1. Power Analysis.** The primary goal of this Phase II study is to demonstrate sufficient superiority of rizatriptan over placebo in the main outcome measure, 1a(1), to warrant a future Phase III trial. In the previous triptan study for VM (see Prior Controlled Study of Triptans for VM), the response rate for active drug was 3/8 (38%) versus 2/9 (22%) for placebo. If the small sample from that failed trial reflected a true response, then the odds ratio favoring the triptan for VM would be 2.1. To improve our estimate, we examined the results of two large registration trials that used a simple randomization design similar to the present proposal to test rizatriptan for conventional migraine. Those studies had response rates of 74% and 77% for rizatriptan versus 28% and 37% for placebo giving odds ratios of 7.4 and 5.7 favoring rizatriptan. The lower response rates in the VM trial most likely reflected the inadequate sample size, but could suggest that triptans are less effective for VM than conventional migraine. To account for this possibility, we took the limited results of Neuhauser, et al. as a worst-case scenario for our sample size calculation. Focusing on the main outcome measure, 1a(1), in this double-blind, randomized trial, with PASS simple randomization design and using a type I error of 0.05, type II error of 0.2 (equivalent to power of 80%), two-sided tests, then treating 120 subjects (with 2:1 ratio for treatment and placebo) will allow us to detect an odds ratio as small as 3.2. Thus, the plan to enroll 200 subjects in the Observation Phase and select 120 for the Treatment Phase will be sufficient, even if the response of VM to rizatriptan proves to be only half that of conventional migraine. Phase II trials typically gather data on secondary outcomes (e.g., 1a(2)-1d(2)) and other variables (2a-c) to inform the design of Phase III trials, but sample sizes need not be planned to demonstrate significant differences in these variables.

**2. Randomization.** A randomization scheme will be developed to assign the 120 patients expected to be included in the Treatment Phase to parallel treatment arms in a 2:1 ratio of active drug:placebo.

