4. We will use this 3-step analysis procedure to test all outcome measures for hypotheses 1a-1d. However, the principal result of the study will be determined by the findings of bivariate analyses and multivariate modeling of the main outcome measure, 1.a.(1), plus favorable findings on tolerability measures, 1d(1)-1d(2). We will include all subjects who treat at least one vertigo attack with study drug (i.e., intent-to-treat analysis). A statistically significant result favoring rizatriptan over placebo on 1a(1) and absence of statistically significant differences on 1d(1)-1d(2) will support development of a Phase III clinical trial of rizatriptan for treating vestibular attacks in patients with VM. The design of future trials will also be informed by results of tests of secondary measures 1a(2)-1c(2). We did not hypothesize equal tolerability for rizatriptan and placebo, but rather an absence of significantly higher rates of serious adverse effects and drug-related treatment discontinuation, so our statistical analyses of measures 1d(1)-1d(2) will not include equivalence tests.

[figure not shown]

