7. Interim analysis: We will conduct an interim analysis at study midpoint without breaking the blind to assess (1) recruitment, (2) safety, and (3) efficacy. Plans for shortfalls in recruitment are noted below. We will terminate the study for insufficient safety if there is a statistically significant difference between arms in adverse events of greater than minor severity, or for lack of efficacy if response rates are <25% in both arms, i.e., no better than placebo rates in previous triptan trials. We will continue the study if the primary outcome, 1(a)1, is >25% in at least one arm, but not statistically different between arms. If the primary outcome is statistically different, then we will terminate the study because the primary aim will be met. We will break the blind and identify the results as positive (rizatriptan superior to placebo) or negative (rizatriptan inferior to placebo).

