## **K. Timeline of Study**

During the first three months of the study, we expect to finalize data entry methods and train study personnel. Then we will begin recruitment into the Observation Phase. Patients will remain in the Observational Phase until they have two qualifying attacks or for a maximum of 12 months. These phases will continue for a total of four years. Subjects who are active in the Treatment Phase at month 57 will be scheduled for a Final Visit (Visit 3) regardless of how many attacks they have treated. We will conduct reviews every 3 months to evaluate enrollment and the flow of subjects through all parts of the study to determine whether recruitment efforts have to be extended and to examine safety data with the DSMB. Analysis of data from the Observation Phase will begin as soon as that portion of the study is closed. Interim analysis will occur at month 33. Analysis of treatment outcome data will commence after the last subject has a Final Visit.

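### The midpoint efficacy stop has no boundary and the final test has no adjusted level; testing at 0.05 both times puts two-sided type I error at about 6.6–8.5%, not 5%

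*Combined protocol and SAP*

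**What the plan says.** Section III.J.3, item 7 plans one interim analysis at the study midpoint, with three outcomes for efficacy:

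- Stop as a success or as a harmful result: "If the primary outcome is statistically different, then we will terminate the study because the primary aim will be met". The blind is then broken and the finding labelled positive or negative according to its direction.
- Stop "for lack of efficacy if response rates are <25% in both arms".
- Continue: "We will continue the study if the primary outcome, 1(a)1, is >25% in at least one arm, but not statistically different between arms".

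Section III.K fixes the timing by calendar ("Interim analysis will occur at month 33") and places the main analysis at the end: "Analysis of treatment outcome data will commence after the last subject has a Final Visit". Item 4 of III.J.3 makes significance of outcome 1a(1) in favour of rizatriptan, together with acceptable tolerability, the basis for supporting Phase III. The only error rate is in III.J.1: "using a type I error of 0.05, type II error of 0.2 (equivalent to power of 80%), two-sided tests". Sections III.J and III.K give no interim critical value, spending function or adjusted final level.

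**The concern.** Two tests can each declare the primary aim met. If each is run at the only level the plan states, the chance that at least one is significant under the null exceeds 5%. The power calculation allows for one look only. Because the look falls at a fixed month, the share of information then available is unknown in advance, so a boundary fixed for one fraction would not be enough either.

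The two stopping rules also have no stated order, and the same data can meet both. One reading then ends the trial as a failure and the other as a success.

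At stake is the decision that the trial exists to inform, namely whether 1a(1) supports a Phase III trial.

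**Working it through.** **Inputs.** From III.J.1: two-sided 0.05; 80% power; 120 subjects at 2:1 (80 vs 40); detectable odds ratio 3.2; placebo rates 22% ("the response rate for active drug was 3/8 (38%) versus 2/9 (22%) for placebo"), 28% and 37%. From III.J.3 item 2: chi-square for categorical outcomes. From item 7: the stopping rules. Assumptions: 0.05 at both looks; half the information at the interim, i.e. 40 vs 20 subjects, or 120 vs 60 attacks at three per subject, taken as independent; no continuity correction.

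**1. The plan's own figure.** With 22% on placebo and odds ratio 3.2, the odds on rizatriptan are (0.22/0.78) × 3.2 = 0.903, a rate of 47.4%. Then:

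- pooled rate (80 × 0.474 + 40 × 0.22)/120 = 0.390
- null SE = √[0.390 × 0.610 × (1/80 + 1/40)] = 0.0944
- alternative SE = √[0.474 × 0.526/80 + 0.22 × 0.78/40] = 0.0861
- power = Φ[(0.254 − 1.96 × 0.0944)/0.0861] = 79.0%

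The plan's 80% is therefore reproduced as a single-look design.

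**2. Two looks at 0.05, normal theory, no credit for the 25% stop.** The interim and final z-statistics are bivariate normal with correlation √t, where t is the information fraction. The error is 1 − P(|Z₁| < 1.96 and |Z₂| < 1.96).

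| t | Two-sided | False superiority |
|---|---|---|
| 0.25 | 9.1% | 4.5% |
| 0.50 | 8.3% | 4.2% |
| 0.556 | 8.1% | 4.1% |
| 0.75 | 7.3% | 3.7% |

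The value 0.556 is the share of months 3–57 elapsed at month 33: (33 − 3)/(57 − 3) = 30/54.

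**3. Exact enumeration with the 25% stop obeyed.** The test is z = (p̂₁ − p̂₀)/√[p̄(1 − p̄)(1/n₁ + 1/n₀)], with |z| ≥ 1.96 at each look. For every pair of interim counts, the binomial probability is added to the error if the interim test rejects. If the trial continues, that probability is multiplied by the chance of rejecting at the final look. Ranges cover subject and attack counts and both orders of the two stops.

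| Common rate | Two-sided | False superiority |
|---|---|---|
| 15% | 1.5–5.7% | 0.1–2.3% |
| 22% | 6.6–7.5% | 2.6–3.2% |
| 28% | 8.2–8.4% | 3.8–4.0% |
| 37% | 8.4–8.5% | 4.1–4.2% |

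A single look of the same test gives 5.0–5.1% two-sided at 22–37%. If the 25% stop is ignored, the two-look figure at those rates is 8.2–8.5%. On subject counts the stop ends about 33% of null trials at 22%, 8% at 28% and 0.3% at 37%, which is why it offers little protection at the higher rates.

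**4. Conflict between the rules.** Take 29/120 (24.2%) against 7/60 (11.7%). The pooled rate is 36/180 = 0.20, the SE is √[0.16 × (1/120 + 1/60)] = 0.0632, and z = 0.125/0.0632 = 1.98, p = 0.048. Both arms are below 25% and the arms differ significantly, so both stops apply.

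**5. A boundary that holds the level.** O'Brien-Fleming-type spending at t = 0.5 gives interim p<0.003 and final p<0.049. By exact enumeration, without credit for the 25% stop, two-sided error is 4.9–5.0% at 22%, 5.0% at 28% and 5.0–5.1% at 37%.

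**The case against.** **The 25% stop already protects the trial, and only superiority matters.** The stop is credited in the table. At 22%, the only rate from a vestibular migraine trial, false superiority is 2.6–3.2%, an excess of 0.1–0.7 points; at 15% it is below 2.5%. The larger excess arises at 28% and 37%, which come from conventional migraine. This stands as a limit on size. However, item 7 also declares negative results, so the two-sided count is relevant, and it exceeds 5% at all three cited rates.

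**The size depends on the test.** It does. With subject counts and the 25% stop obeyed, Fisher's exact test gives 5.7–6.6%. A Yates-corrected chi-square gives 3.8–4.6%, but only because its single-look size is already 2.7–3.0%. The plan names neither.

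**The final decision is not one test.** Item 4 of III.J.3 combines bivariate tests with modelling and tolerability. Requiring the bivariate and model results to agree would lower the final-look error; accepting either would raise it. The tolerability condition can only lower it. The decimals are therefore conditional.

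**The low end rests on independent attacks.** The 6.6% needs attack counts with the 25% stop read first. On the plan's 120 subjects the range is 7.2–8.5%.

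**The rule conflict is rare.** Under the null both stops apply in 0.3% (subjects) or 0.6% (attacks) of trials at 22%, and in at most 0.03% at 28%. It is a drafting gap with little effect on the error rate.

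**It is a Phase II trial with a null result.** A false positive would have led to another trial, not to a change in practice, and the reported primary outcome was not significant. That limits the consequence but does not make the rule sound.

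**Conclusion.** The concern holds. The plan permits success at either of two tests and states only a single-look 5%. Under the assumptions listed, two-sided error is 6.6–8.5% across the placebo rates the plan cites. False superiority is 2.6–4.2% against 2.5%: a small excess near 22%, and more than half again the nominal rate at 28–37%. The main assumption is 0.05 at both looks, which the plan leaves as the only available reading. The direction is robust to the information fraction and to using Fisher's test, but not to a Yates correction. Because the rule governs the primary decision, it must be corrected. The reported outcome is not called into question.

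**What to change.** In III.J.3, item 7:

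1. Allow an efficacy stop only at a prespecified group-sequential boundary, for example O'Brien-Fleming-type spending at two-sided 0.05, with interim p<0.003 and final p<0.049 at half the information. Recompute it at the actual fraction: 0.0008/0.0497 at 40%, 0.0053/0.0483 at 56%, 0.019/0.044 at 75%.
2. State that this boundary is read before the 25% rule. With 40 vs 20 subjects the smallest p-value when both arms are below 25% is 0.0034, so the boundary at half the information already removes the overlap there; the sentence covers other counts.

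**Cost.** The change is wording only, and the maximum stays at 120 subjects. At 47.4% vs 22%, exact power is 79.5% with the boundary and 79.4% for a single look; the 0.1-point difference comes from discreteness. By normal theory an 80.0% single-look design falls to 79.9%, and 0.4% more subjects (120 × 0.0038, about half a subject) would restore it.

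Against two unadjusted looks, power falls from 81.7% to 79.5%, the difference having been bought partly with the excess error. Early efficacy stops at the design effect fall from about 50% to about 12%. Counting efficacy stops only, expected subjects rise from 120 − 60 × 0.501 = 89.9 to 120 − 60 × 0.117 = 113.0, about 23 more on average.

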## **K. Timeline of Study**

During the first three months of the study, we expect to finalize data entry methods and train study personnel. Then we will begin recruitment into the Observation Phase. Patients will remain in the Observational Phase until they have two qualifying attacks or for a maximum of 12 months. These phases will continue for a total of four years. Subjects who are active in the Treatment Phase at month 57 will be scheduled for a Final Visit (Visit 3) regardless of how many attacks they have treated. We will conduct reviews every 3 months to evaluate enrollment and the flow of subjects through all parts of the study to determine whether recruitment efforts have to be extended and to examine safety data with the DSMB. Analysis of data from the Observation Phase will begin as soon as that portion of the study is closed. Interim analysis will occur at month 33. Analysis of treatment outcome data will commence after the last subject has a Final Visit.

## **L. Feasibility and Limitations**

The primary hindrance to successful completion of this study will be patient recruitment and retention. Rizatriptan has a proven track record of safety in thousands of patients over more than a decade of clinical use, so we do not expect significant problems with medication intolerance. The study of zolmitriptan by Neuhauser, et al., demonstrated the pitfalls of a triptan trial for patients with VM. Just 26% of enrolled subjects were randomized to treatment because they did not continue to have active vestibular attacks. We believe that we will substantially increase that randomization rate by enrolling only subjects with more active illness, as described in "Considerations for Improved Subject Selection for the Current Proposal." The previous investigators excluded 12% of subjects for coexisting medical problems. We expect to stabilize coexisting medical problems such as uncontrolled hypertension or anxiety disorders during our 12 month Observation Phase, allowing us to retain a higher percentage of enrolled subjects. Neuhauser, et al., also excluded 14% of subjects from randomization because they lived too far from the study center. Geographic barriers are much less of a problem for medical care in 2013 than they were in 2003. Both of our centers have expanded the reach of patient care through electronic communications and other secure technologies, eliminating the need for a geographic exclusion. These factors and the improvements in study design based on the five-point examination of shortcomings in the zolmitriptan trial (see "Prior Controlled Study of Triptans for Migraine-Associated Vertigo") should allow us to successfully randomize 50% of enrolled subjects into the Treatment Phase of this study. Keeping in mind that the sample size calculation reflected the worst-case scenario (100 subjects for the Treatment Phase), then we will have to recruit a maximum of 200 subjects into the Observation Phase. Our recently published studies indicate that we see approximately 200 new patients with VM at our two centers annually. A record review suggests that half of those would likely meet study inclusion criteria. Therefore, we expect to examine 400 potential subjects during the 4 years of active enrollment. Study success would require us to recruit 50% of those patients. The Mayo Clinic team has enrolled 79.3% of eligible patients into a currently active trial of sertraline versus verapamil for patients with VM/CSD, which demonstrates our ability to achieve needed enrollment. Subjects entering the current Mayo study have almost no experience with triptans. Most have been prescribed vestibular suppressants (e.g., meclizine) for acute attacks, meaning that we will lose almost no subjects due to prior rizatriptan treatment. (N.B. – The current Mayo study will not compete with this proposal. Its inclusion criteria target chronic, not acute, symptoms).

## **M. Plans to Address Limitations**

The patient flow just reviewed suggests that we will be able to meet study recruitment and retention targets. However, we intend to examine rates of enrollment into the Observation Phase and randomization into the Treatment Phase every quarter. If we fall short of targets for enrollment or randomization at any point, we will take three steps, as needed. (1) Contact patients with VM who were previously examined at our institutions. Both centers maintain databases of patients who participated in previous diagnostic studies (N>400), many of whom expressed interest in treatment trials. (2) The Mayo Clinic site will expand recruitment to the Mayo Clinic Health System of hospitals and clinics across a three-state area of the upper Midwest, and UCLA will expand recruitment to affiliated hospitals and clinics across Southern California. (3) Both sites will advertise selectively to regional and local professional organizations, patient advocacy groups, and the general public.

A negative treatment result (i.e., finding that rizatriptan is not superior to placebo) will not be a study failure. Rather, it will be evidence that rizatriptan lacks the efficacy needed to pursue a Phase III trial in patients with VM. A negative result will prompt a search for other abortive and prophylactic therapies for VM and might nudge researchers to re-evaluate the concept of VM as a migrainous phenomenon. Data collected for Specific Aim #2 should be helpful in considering alternative medications and different potential pathophysiologic processes for VM regardless of the efficacy of rizatriptan.

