## **F. What are the pharmacokinetics and costs of rizatriptan versus other triptans?**

Rizatriptan is rapidly and near completely absorbed (~90%) from the gastrointestinal tract following administration of the oral tablet. Absolute bioavailability is 47% owing to moderate first-pass metabolism. The mean time to maximum plasma concentration ( $t_{max}$ ) following a single rizatriptan 10-mg tablet in healthy volunteers is about 1 hour, which is shorter than that of other triptans. Rizatriptan has a relatively short plasma half-life of approximately 2–2.5 hours. Healthy males showed no unexpected accumulation of

rizatriptan following administration of multiple 10 mg doses. Rizatriptan is also available in a wafer form that dissolves in the mouth but it is absorbed at a slower rate than the oral tablets (mean  $t_{max}$  1.6–2.5 hours).

Rizatriptan is eliminated primarily via oxidative deamination catalyzed by monoamine oxidase A and renal elimination which together account for 76% of total plasma clearance. Cytochrome P-450 inhibitors minimally affect rizatriptan pharmacokinetics, reducing a major source of potential drug-drug interactions. Patients receiving propranolol may have an increase in plasma rizatriptan concentration, possibly reflecting competitive inhibition of monoamine oxidase A. Rizatriptan crosses the blood-brain barrier better than other triptans. Though other triptans can be administered intranasally or by injection, rapidly absorbed oral rizatriptan is a logical, cost-effective choice for this first phase II study. Rizatriptan is now available in generic formulation, making it a cost-effective option for future clinical care. If oral rizatriptan is effective for treating vertigo attacks in VM, then other routes of administration can be assessed in later studies.

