## III. APPROACH

We propose a two-center, randomized, double blind, placebo-controlled, parallel, three-episode, clinical trial of rizatriptan 10 mg oral tablets versus placebo for treating spontaneous vestibular attacks in patients with VM.

Our primary Specific Aim is to test hypotheses 1a-1d that rizatriptan will be:

- 1a. Superior to placebo in reducing the severity and duration of vestibular attacks as measured by:
  - (1) Proportion of treated attacks in which subjects experience a reduction in severity rating from Grade 3/2 to Grade 1/0 at one hour after taking study medication (see below for rating description). This is the main outcome measure; 1a(2)-1d(2) are secondary outcome measures.
  - (2) Proportion of treated attacks in which subjects achieve sustained relief (i.e., vestibular symptom severity rating of Grade 1/0) for 24 hours after taking study medication, without use of non-study therapies.
  - (3) Proportion of treated attacks in which subjects experience freedom from vestibular symptoms (i.e., severity rating of Grade 0) at one hour after taking study medication.
  - (4) Use of fewer non-study therapies after each attack treated with study medication.
- 1b. Superior to placebo in reducing severity of symptoms associated with vestibular attacks as measured by:
  - (1) Proportion of treated attacks in which subjects experience relief (reduction to Grade 1/0) from VM-associated symptoms (e.g., nausea, vomiting, motion sensitivity, gait disturbance, headache, photophobia, and phonophobia) at one hour after taking study medication.
  - (2) Proportion of treated attacks in which subjects achieve sustained relief from VM-associated symptoms for 24 hours after taking study medication without use of non-study therapies.
- 1c. Superior to placebo on treatment satisfaction and health-related quality of life as measured by:
  - (1) Scores on the Treatment Satisfaction Questionnaire for Medication (TSQM) at 48 hours after each attack treated with study medication
  - (2) Scores on the Short Form 12 (SF-12) at 48 hours after each attack treated with study medication
- 1d. Tolerated as well as placebo by patients with VM as measured by:
  - (1) No greater rate of treatment-emergent serious adverse events reported on the NCI Common Toxicity Criteria Scale 4.0^59 obtained 48 hours after each attack treated with study medication.

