7. **Patient Health Questionnaire (PHQ-9).** A 9 item self-report rating scale for depression, another common comorbidity of VM. The PHQ-9 has cut-offs for clinically significant levels of depressive symptoms.
8. **NEO-PI-3 Personality Inventory (NEO-PI-3).** A 240-item questionnaire that assesses traits of the Five Factor Model of personality (neuroticism, extraversion, openness, agreeableness, conscientiousness).

**F. Handling of Study Drug.** The Mayo Clinic Research Pharmacy will support both study sites. The research pharmacists will purchase rizatriptan 10 mg tablets from a commercial supplier. Unaltered rizatriptan tablets will be encapsulated. Look-alike lactose-containing placebo capsules will be manufactured in the Mayo Clinic Pharmacy Production Laboratory following Good Manufacturing Practices. For patients who are allergic to lactose, carboxymethyl cellulose will be used instead of lactose. All capsules will be labeled with NDC numbers so that active drug and placebo can be identified. Randomization codes will be entered into the Research Pharmacy record. When prescriptions for study drug are received from physician investigators, drug or placebo will be placed into prescription bottles with required labeling. Prescriptions will be verified and cross-checked against the Research Pharmacy record for each subject. Then the prescription will be dispensed to subjects or mailed to their homes. Subjects will return used and unused bottles to verify medication accuracy and adherence. Should any questions arise after study drug is dispensed, the research pharmacists will be able to identify study drug for each subject by cross referencing the NDC numbers and randomization codes. Research pharmacists will maintain drug logs and all other applicable regulatory paperwork.

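### A null result at 1 hour with the encapsulated tablet cannot by itself show that rizatriptan lacks the efficacy needed for Phase III

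*Combined protocol and SAP*

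**What the plan says.** - **Conclusion attached to a null.** Section III.M treats any finding that rizatriptan is not superior as a negative result and states: "Rather, it will be evidence that rizatriptan lacks the efficacy needed to pursue a Phase III trial in patients with VM". It adds that such a result "might nudge researchers to re-evaluate the concept of VM as a migrainous phenomenon".
- **Outcome that decides.** Section III (Approach) makes 1a(1) the only main outcome: the proportion of treated attacks with "reduction in severity rating from Grade 3/2 to Grade 1/0 at one hour after taking study medication". Section III.J.3, item 4, rests the principal result on 1a(1) plus tolerability.
- **Absorption.** Section I.F gives the mean time to peak level as "following a single rizatriptan 10-mg tablet in healthy volunteers is about 1 hour". Of the wafer it says that "it is absorbed at a slower rate than the oral tablets", and it concludes that "rapidly absorbed oral rizatriptan is a logical, cost-effective choice for this first phase II study". The half-life is given as 2-2.5 hours.
- **Product given.** Section III.F: "Unaltered rizatriptan tablets will be encapsulated". Nothing is said about how this affects absorption.
- **Other medication.** Sections III.D.4 and III.G allow it from 1 hour after the dose. The stated reason is to protect the primary outcome.
- **Later ratings.** Symptoms are also rated at 2, 4, 24 and 48 hours (section III.D.4). Section III.J.3, item 2, compares the arms at each time point, and item 3 models severity over time. The named later outcomes on vestibular attacks are 1a(2), relief sustained for 24 hours without other therapies, and 1a(4), use of other therapies.

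**The concern.** Section III.M turns non-superiority into evidence about the drug. That step needs a reading late enough for the drug to have acted and a sample large enough that a real effect would seldom be missed. The plan argues neither.

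The reading falls at about the mean peak time of a plain tablet, in people who were not having an attack, while the trial product must first leave a capsule. No relief outcome is defined between 1 and 24 hours. The 2-hour comparison that the plan does allow has no rule for rescue, so relief from a non-study drug would be credited to the assigned arm.

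At stake is the decision whether to go on to Phase III and, by the plan's own words, the standing of VM as a form of migraine. The interim rule (section III.J.3, item 7) can also stop the trial for lack of efficacy if response is below 25% in both arms, and it ties response to 1a(1).

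**Working it through.** **1. The plan's own figure.** Inputs from section III.J.1: 120 subjects at 2:1 (80 and 40), two-sided 0.05, 80% power, detectable odds ratio 3.2. The placebo rate behind 3.2 is not stated; I take 22%, the rate from the earlier triptan trial in VM.

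Formula (pooled two-proportion test): power = Φ[(d − 1.96·s0)/s1], with s0 = √[p̄(1−p̄)(1/40+1/80)] and s1 = √[p1(1−p1)/40 + p2(1−p2)/80].

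An odds ratio of 3.2 on 22% gives odds 0.282 × 3.2 = 0.903, or 47.4%. Then p̄ = 0.390, s0 = 0.0944, s1 = 0.0861, and (0.254 − 0.185)/0.0861 = 0.805. Power is 79%. The odds ratio detectable at exactly 80% is 3.24. The stated 3.2 is reproduced.

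**2. Power at the plan's worst case.** Section III.J.1 names 3/8 (38%) against 2/9 (22%), odds ratio 2.1, as its worst case.
- 38% against 22%: p̄ = 0.327, s0 = 0.0908, s1 = 0.0851, (0.160 − 0.178)/0.0851 = −0.212. Power 42%.
- 3/8 against 2/9, unrounded: (0.1528 − 0.1776)/0.0852 = −0.292. Power 39%.

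About 294 to 321 subjects would be needed for 80%. The outcome counts attacks, so repeats help. With three attacks each, effective N = 360/(1 + 2·ICC), and the ICC is assumed:

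| ICC | Effective N | Power |
|---|---|---|
| 0.1 | 300 | 77-81% |
| 0.3 | 225 | 65-69% |
| 0.5 | 180 | 54-58% |
| 0.7 | 150 | 47-50% |

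**3. If only part of the effect shows at 1 hour.** Take the odds ratio of 3.2 (22% to 47.4%) and assume the share visible at 1 hour. All of it gives 79% power; three quarters (41.1%) gives 55%; half (34.7%) gives 29%.

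**4. What a capsule delay could do.** One-compartment model: C(t) ∝ e^(−kt) − e^(−ka·t), with k = ln 2/half-life and ka set so that the peak is at 1 hour (ka = 2.19 for a 2-hour half-life, 2.46 for 2.5 hours). With no delay, 16-18% of total exposure has accrued by 1 hour. The delay is an assumption, since the documents give none:

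| Assumed delay | 1-hour level, % of peak | Exposure 0-1 h, % of no-delay value |
|---|---|---|
| 15 min | 97 | 67 |
| 30 min | 85-86 | 35-36 |
| 45 min | 57-58 | 11 |

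Example, half-life 2 hours and 15 minutes: C(0.75)/C(1) = (0.771 − 0.193)/(0.707 − 0.112) = 0.578/0.595 = 0.97.

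**5. What a null could exclude.** Suppose both arms show 22%. At subject level the standard error of the log odds ratio is √(1/8.8 + 1/31.2 + 1/17.6 + 1/62.4) = 0.467, so the upper 95% limit is e^(1.96 × 0.467) = 2.50, which does not exclude 2.1. With three attacks and ICC 0.3 the standard error falls by √(120/225) to 0.341 and the limit to 1.95, which does. With ICC 0.7 it falls by √(120/150) to 0.418 and the limit is 2.27, which does not.

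**The case against.** - **Rescue from 1 hour spoils the primary.** A reader might infer this. It does not: the waiting time keeps other drugs out of the 1-hour reading. It affects only later ratings.
- **Subjects are scored before the drug can act.** This is the tempting strong reading, and the documents do not support it. One can assume a lognormal peak time with mean 1 hour and CV 30-70% and find that 38-44% of doses peak after 1 hour. That is only the part of a skewed distribution above its own mean, and a dose can be near its peak level before it peaks. With a 15-minute delay the typical 1-hour level is still about 97% of peak. Neither the CV nor the delay is in the documents.
- **The tablet was chosen over the wafer for its peak time.** This is implied at most. The stated grounds are rapid absorption and cost.
- **Later evidence is planned.** This stands in part. 1a(2) counts rescue as failure, 1a(4) reflects what happens once rescue is allowed, and the mixed models use all time points. None is a defined relief outcome between 1 and 24 hours.
- **Section III.M speaks only of the efficacy needed for Phase III, and secondary results also inform later trials.** This is fair as a go/no-go statement. Its next sentence goes further, however, and the statement carries no condition on time point, product or precision.
- **The appended results confirm early scoring.** They do not. Vertigo relief at 1 hour was numerically worse on rizatriptan (47.7% against 57.6%), whereas early reading predicts a diluted benefit. The 24-hour difference (80.5% against 59.1%) is for unsteadiness/dizziness only, is one of several secondary results, and is described without the no-rescue condition. The summary itself concludes limited benefit, not absence of efficacy.

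**Conclusion.** The point holds as one about inference. A null 1a(1) shows that no effect was demonstrated at 1 hour with the encapsulated tablet. On its own it does not show that rizatriptan lacks the efficacy needed for Phase III.

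The firmer ground is power. At the plan's own worst case a null is more likely than not on the subject-level calculation (power 39-42%), and still common with three attacks per subject (power 47-69% at ICC 0.3-0.7). These figures rest on the rates in section III.J.1, a pooled two-proportion test and, for repeated attacks, an assumed ICC and full use of three attacks.

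The timing ground is weaker. Under the assumed delays the effect on drug exposure at 1 hour runs from minor to large, and the documents do not say which applies. It is a gap in the plan, not a demonstrated failure, and it does not invalidate 1a(1) as a measure of relief at 1 hour.

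**What to change.** 1. Keep 1a(1) at 1 hour and leave the rescue permissions as they are.
2. Add one secondary outcome: Grade 1/0 at 2 hours after the dose without non-study therapy, with rescue before 2 hours counted as non-response. The diary already supplies the data. If it is added once results are known, label it post hoc. State its limits: it will miss slow responders who take rescue at 1 hour, and because qualifying attacks need last only 2 hours, it will include more spontaneous recovery than the 1-hour reading.
3. Reword section III.M so that a null 1a(1) is reported as no effect shown at 1 hour with the encapsulated product. Conclude lack of efficacy only if the confidence interval, allowing for repeated attacks, excludes an effect worth pursuing; the plan's own odds ratio of 2.1 is one candidate. Requiring a null at both 1 and 2 hours would not do, since that still takes non-significance for absence of effect.
4. State in sections I.F and III.F that the 1-hour peak time refers to the unencapsulated tablet.

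The cost is wording, one more analysis of existing ratings, one more secondary outcome, and a less sweeping conclusion from a negative trial. The interval may prove too wide to settle the matter, in which case the report should say so.
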